APPENDIX E: RAND-36 ITEM SHORT FORM SURVEY	50
APPENDIX F: QUICK DASH QUESTIONNAIRE	54

List of Abbreviations

[figure not shown]
ADR	Adverse Drug Reaction
AE	Adverse Event/Adverse Experience
cc	Cubic Centimeter
CNS	Central Nervous System
CRF	Case Report Form
DASH	Disability of the Arm, Shoulder, and Hand
DATA	Device and Technique Assessment
DIEP	Deep Inferior Epigastric Perforator
HIPAA	Health Information Portability and Accountability Act
ICH	International Conference on Harmonization
ID	Identification
IRB	Institutional Review Board
IV	Intravenous
mg	Milligram
mL	Milliliter
PCA	Patient-Controlled Analgesia
PO	By Mouth (Latin: Per os)
POE	Provider Order Entry (System)
PSEF	Plastic Surgery Education Foundation
PSI	Pounds per Square Inch
RAND	Research and Development
SAE	Serious Adverse Event
SEER	Surveillance, Epidemiology, and End Results
TRAM	Transverse Rectus Abdominus Myocutaneous

1. Protocol Summary

Full Title	Use of Pre-operative Paravertebral Blocks to Decrease Post-operative Pain Following Mastectomy with Immediate Tissue Expander Reconstruction
Short Title	Paravertebral Blocks to Decrease Breast Reconstruction Pain
Study Type	Prospective, Randomized, Double-Blind Clinical Trial
Conducted By	The Department of Plastic and Reconstructive Surgery Johns Hopkins University School of Medicine
Principal Investigator	[name].
Sample Size	Enrolled: 70 (Randomization Treatment: Placebo = 35:35)
Study Population	
 • Women aged 18-75 years. • Choose bilateral mastectomy followed by immediate tissue expander breast reconstruction. • Have no inflammatory breast cancers. • Be aware of the nature of her malignancy. • Understand the study purpose, requirements, and risks. • Be able and willing to give informed consent.
Accrual Period	Two Years
Study Design	
Double-blind, randomized, controlled clinical trial comparing patient-reported pain and pain medication/opioid use between patients randomized to ropivacaine (treatment) pre-operatively placed paravertebral blocks or subcutaneous paravertebral saline (placebo) injections. Candidates will have elected to undergo bilateral post-mastectomy immediate tissue expander breast reconstruction. Participants meeting inclusion criteria will be enrolled and baseline data collection completed prior to randomization and surgery.
 
Patients will be randomized 1:1 to ropivacaine- (treatment) paravertebral blocks or subcutaneous saline-(placebo) paravertebral injections in a double-blinded design. Patient-specific surgical details will be recorded intraoperatively. Following the surgery, post-operative pain, pain medication/opioid use, and the occurrence of adverse events (AEs)/serious adverse events (SAEs) will be assessed on Days 1, 2, and 3. A clinic visit occurs on Day 7 when additional data are collected (updated medical history, pain medication/opioid use, AEs/SAEs, and study questionnaires).
 
Long-term quality-of-life/health outcomes assessments will be done on post-operative Day 90 (± 14 days), Year 2 (± 14 days), and Year 4 (± 14 days). The Year 2 and Year 4 follow-ups are included as tertiary endpoints to capture differences in chronic pain, and patients will be asked to complete the same questionnaires as at the Day 90 follow up.

Study Duration	Four years from initial qualifying surgery.

Study Agent/Intervention Description	Ropivacaine (treatment) pre-operatively placed paravertebral blocks or subcutaneous paravertebral saline (placebo) injections.
Primary Objective	To determine if post-operative static pain scores differ between women undergoing bilateral mastectomy followed by bilateral immediate tissue expander breast reconstruction randomized either to ropivacaine-(treatment) pre-operatively placed paravertebral blocks or subcutaneous paravertebral saline (placebo) injections.
Secondary Objectives	To determine if post-operative moving pain scores, opioid use, nausea, sleep interference and length of hospital stay differ between women undergoing bilateral mastectomy followed by bilateral immediate tissue expander breast reconstruction randomized either to ropivacaine-(treatment) pre-operatively placed paravertebral blocks or subcutaneous paravertebral saline (placebo) injections.
Tertiary Objectives	To determine if long-term changes in Quality of Life scores [the RAND-36 Health Survey, Disability of the Arm, Shoulder, and Hand (Quick DASH) questionnaire, and Breast-Q scores] differ between women undergoing bilateral mastectomy followed by bilateral immediate tissue expander breast reconstruction randomized either to ropivacaine-(treatment) pre-operatively placed paravertebral blocks or subcutaneous paravertebral saline (placebo) injections.

2. Schema

3. Rationale

Immediate breast reconstruction following mastectomy, when compared with delayed reconstruction or no reconstruction, has been shown to have superior results for both aesthetics and psychometric outcomes^{1,2}, and is less expensive than delayed breast reconstruction.³ Additionally, the type of breast reconstruction (implant versus autologous) can affect psychosocial outcomes.⁴ However, the percentage of patients who undergo immediate reconstruction following mastectomy for breast cancer remains low. The national average from the SEER database in 1998 was 15%⁵, while an evaluation of the Maryland Hospital Discharge Database for 1995 through 2005 found that 28% of women in the state of Maryland had immediate breast reconstruction following mastectomy.⁶ These low rates may be because patients who have mastectomy and immediate placement of tissue expanders for reconstruction have much more pain than patients who have mastectomy alone.⁷

Finding appropriate and safe ways to control post-operative pain is important. While adding non-steroidal anti-inflammatory drugs can decrease pain, it seems to increase complications. A randomized trial has shown that diclofenac significantly decreases pain and opioid use following mastectomy and immediate breast reconstruction, but significantly increases bleeding.⁸

One randomized, placebo-controlled, blinded trial found significant reductions in pain scores and analgesic consumption as well as earlier return to normal activity and better surgeon and patient satisfaction when preoperative paravertebral blockade with bupivacaine was given along with general anesthesia for varicocele surgery.⁹ A randomized, blinded trial in the setting of Video Assisted Thoracic Surgery, showed significant reductions on postoperative pain scores, decreased cumulative morphine consumption, increased patient satisfaction with analgesia and quicker first mobilization and time to hospital discharge.¹⁰ Similarly, two prospective, randomized placebo-controlled trials (in the settings of hepatectomy¹¹ and retropubic prostatectomy¹²) also showed similar results. Further, at least six prospective randomized trials across several surgical procedures and specialties.^{13, 14, 15, 16, 17, 18} have also shown a significant improvement in postoperative pain with the application of concomitant paravertebral block for analgesia. Some of these trials report on decreased consumption of postoperative analgesics^{16, 14} earlier discharge^{17, 18} and decreased likelihood of complications.¹⁵

In terms of breast surgery, paravertebral blocks have been studied at the breast site mostly after mastectomy. We found two randomized, double-blinded, placebo-controlled trials focused on the mastectomy-only (i.e., no reconstruction) patient population. One of them, by Buckenmaier et al., studied 73 unilateral mastectomy patients and concluded that routine use of a continuous paravertebral block catheter for anesthesia was not supported due to a lack of clinical significance in degree of postoperative pain, nausea, mood state, level of symptom distress, or return to normal activity among the study groups.¹⁹ The second paper, by Moller et al., studied 88 unilateral mastectomy patients with one-time multi-level bupivacaine paravertebral block, but found no statistical difference in pain scores or consumption of analgesics between the study and control groups.²⁰ We also found one prospective, randomized trial that included patients with lumpectomy and mastectomy.²¹ This study by Pusch et al. found that single-injection

paravertebral blocks were quite beneficial and could be used as an alternative to general anesthesia.

We also found two retrospective chart reviews that included tissue expander breast reconstruction patients within their study populations.^{22, 23} One of these studies concluded retrospectively that paravertebral blocks in immediate breast reconstruction with tissue expanders may play an important role for decreasing pain and analgesic usage.²² Overall, these two studies supported the use of paravertebral blocks for analgesia in the breast surgery and breast reconstruction patient population.^{21, 22, 23} Additionally, Coopey et al. concluded retrospectively that preoperative paravertebral blocks in patients undergoing mastectomy followed by immediate reconstruction with tissue expanders or implants significantly reduced length of hospital stay, postoperative nausea and shortened the mean time to conversion to oral opioids.²⁴ Our current proposal is built upon preliminary data gathered from our institution (Table 1). Collectively, patients who received mastectomy-tissue expander reconstruction whom were not offered pre-operative paravertebral block, reported higher incidence of pain complaints during inpatient stay (Table 2). However, we did not find any prospective report focused solely on the use of paravertebral blocks for analgesia in breast reconstruction with tissue expanders, implants or flaps.

Table 1: Number of patients who received pre-operative paravertebral block according to site of breast reconstruction from year 2011-2012

Breast reconstruction site	Paravertebral block (n)	No paravertebral block (n)
Left	9	19
Right	9	18
Bilateral	9	24
Total patients	27	61

Table 2: Analysis of outcome with descriptive statistics

Patient cohorts	Postoperative pain event (P-value)	Duration of inpatient stay (P-value)	Postoperative nausea or vomiting (P-value)
PVB vs non-PVB (Total)	0.039	0.17	0.81
PVB vs non-PVB (Unilateral reconstruction)	0.132	0.19	0.75
PVB vs non-PVB (Bilateral reconstruction)	0.423	0.12	0.23

* P-value of <0.05 is considered significant.

PVB = Paravertebral block

Moreover, to date, we do not know of any prospective, randomized placebo-controlled trials reported in tissue expander-based breast reconstruction patients. In fact, the PSEF Device and Technique Assessment (DATA) committee issued a call for prospective, randomized implanted bupivacaine pain pump studies in 2006.²⁵ We believe, therefore, that prospective, randomized, double blind trials are still warranted to confirm the efficacy and safety of continuous bupivacaine infusion via a pain pump in plastic surgery patients. The innovation of

our study is that paravertebral blocks are similar in philosophy to the pain pumps, but less expensive and with lower risk of infection.

We hypothesize that post-operative static pain scores will be lower in ropivacaine patients vs. placebo patients in women undergoing bilateral mastectomy and bilateral immediate reconstruction with placement of tissue expanders. We believe that post-operative moving pain scores, opioids use, nausea, and sleep interference will be likewise improved. We further hypothesize that this decreased post-operative pain may lead to improvements in long-term health outcomes as measured by validated questionnaires. In the presence of clear need and lack of published studies regarding this precise patient population, it is important to determine if paravertebral blocks do reduce post-operative pain, and improve opioids use, nausea, sleep interference, and length of hospital stay in patients undergoing immediate tissue expander breast reconstruction.

4. Objectives

4.1 Primary Objective

To determine if post-operative static pain scores differ between women undergoing bilateral mastectomy followed by bilateral immediate tissue expander breast reconstruction randomized either to ropivacaine- (treatment) pre-operatively placed paravertebral blocks or subcutaneous paravertebral saline (placebo) injections.

4.2 Secondary Objectives

To determine if post-operative moving pain scores, opioid use, nausea, sleep interference, and length of hospital stay differ between women undergoing bilateral mastectomy followed by bilateral immediate tissue expander breast reconstruction randomized either to ropivacaine- (treatment) pre-operatively placed paravertebral blocks or subcutaneous paravertebral saline (placebo) injections.

4.3 Tertiary Objectives

To determine if long-term changes in Quality of Life scores [(the RAND-36 Health Survey, Disability of the Arm, Shoulder, and Hand (Quick DASH) questionnaire, and Breast-Q scores)] differ between women undergoing bilateral mastectomy followed by bilateral immediate tissue expander breast reconstruction randomized either to ropivacaine- (treatment) pre-operatively placed paravertebral blocks or subcutaneous paravertebral saline (placebo) injections.

5. Investigational Plan

5.1 Summary of Study Design

Participants meeting inclusion criteria will be enrolled and baseline data collection completed prior to randomization and surgery. Baseline data collection includes a general patient history, the Patient Pain Assessment Questionnaire which includes static and moving pain scores as well as nausea and sleep interference scores (Appendix A), the Subjective Pain Survey (Appendix B), the pre-operative Breast-Q (Appendix C), the RAND-36 (Appendix E), and the Quick DASH survey (Appendix F).

Patients will be randomized 1:1 to ropivacaine- (treatment) pre-operatively placed paravertebral blocks or subcutaneous paravertebral saline (placebo) injections in a double-blinded design. Neither the treatment team (the anesthesiologist and the surgeon) nor the patient will know the randomization assignment. The pharmacy will be unmasked.

Patient-specific surgical details will be recorded intraoperatively. Following the surgery, post-operative pain [(measured by the Patient Pain Assessment Questionnaire (Appendix A)], pain medication/opioid use, and the occurrence of adverse events (AEs)/serious adverse events (SAEs) will be assessed routinely by staff during the hospital stay and on Days 2 and 3 by telephone interview with study staff for discharged patients. The typical post-operative length of hospital stay is approximately one day. Participants are to return to clinic for the Day 7 (± 2 days) follow-up visit. At this visit an updated medical history will be completed, pain medication/opioid use recorded, and participant AEs/SAEs assessed. Additionally, participants will complete the following questionnaires: Patient Pain Assessment, RAND-36, and Quick DASH.

Long-term quality-of-life/health outcomes assessments will be done on post-operative Day 90 (± 14 days), Year 2 (± 14 days), and Year 4 (± 14 days). During the Day 90 visit, pain scores (Patient Pain Assessment Questionnaire), pain medication/opioid use, post-operative Breast-Q, RAND-36, and the Quick DASH will be administered. The Year 2 and Year 4 follow-ups are included as tertiary endpoints to capture differences in chronic pain, and patients will be asked to complete the same questionnaires as at the Day 90 follow up.

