5.11 Duration of Study Participation

Study participation continues through Year 4 post-operatively. However, the majority of data collection will occur during the first 7 days after the participant’s immediate tissue expander reconstruction following mastectomy. An additional study visit will occur in clinic at Day 90 (± 14 days), prior to the participant’s undergoing any additional reconstructive breast surgery procedures. Thereafter, follow-up phone interviews will occur at post-operative Year 2 (± 14 days), and post-operative Year 4 (± 14 days).

Participants are to return to clinic for a Day 90 (± 14 days) follow-up visit. To encourage participation, participant parking and a \$15 gift card will be given (or mailed) to participants who complete the Day 90 visit.

If a participant chooses to withdraw, is withdrawn, or refuses to participate through Day 90, all efforts will be made to collect all Day 90 post-operative data at the time of study withdrawal. Reasons for premature participation/treatment withdrawal will be recorded to the best of the study team’s ability. Reasons for early withdrawal may include the following:

1. Unanticipated or serious adverse events.
2. Inter-current illness that prevents further administration of treatment or would affect assessment of clinical status to a significant degree.
3. Subject becomes pregnant.
4. Subject refuses to continue treatment.
5. Any reason the study physician deems it necessary for the benefit of the participant.
6. Subject is lost to follow-up.

6. Study Calendar

Table 3. Calendar of study events/procedures.

Parameter	Pre-Study	Surgery (Day 0)	Day1	Day 2*	Day 3*	Day 7 (± 2 days)	Day 90 (± 14 days)	Post-Op Years 2 & 4 (± 14 days)
General Patient History Form	X							
Update Medical History		X	X			X	X	X
Treatment administration (Ropivacaine/Placebo)		X						
Intra-Operative Case report Form (CRF)		X						
Adverse Events of Interest/SAE Assessment		X	X	X	X	X	X	
Pain Meds/Opioid Use	X		X	X	X	X	X	
Questionnaires								
Patient Pain Assessment Questionnaire	X		X	X	X	X	X	X

Subjective Pain Survey	X							
BREAST-Q [®] , Pre-Op	X							
BREAST-Q [®] , Post-Op							X	X
RAND-36 Questionnaire	X					X	X	X
Quick DASH Questionnaire	X					X	X	X

Note: Additional tests may be performed at the discretion of the treating investigator as clinically indicated.

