10.1.3 Tertiary Objectives

To determine if long-term changes in Quality of Life scores [the RAND-36 Health Survey, Disability of the Arm, Shoulder, and Hand (Quick DASH) questionnaire, and Breast-Q scores] differ between women undergoing bilateral mastectomy followed by bilateral immediate tissue expander reconstruction randomized either to ropivacaine- (treatment) pre-operatively placed paravertebral blocks or subcutaneous paravertebral saline (placebo) injections.

This data will be collected via validated questionnaires through patient interviews at 3-months, 2-years, and 4-years (± 14 days) after surgery.

Once enrolled in the study, participants will be encouraged to remain in the study for the 4 years following surgery in order to get final pain scores and quality-of-life/health outcome survey information. Participants who cannot be contacted after several phone attempts and the sending of 2 certified letters via US Postal Service for 3-month, 2-year, and/or 4-year outcome assessments will be considered lost to follow-up.

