Appendix A: Patient Pain Assessment Questionnaire

[figure not shown]
Subject Number: _____ **Study Personnel:** _____

Last Name: _____ **First Name:** _____

MRN: _____ **DOB:** _____ **Date:** ___/___/___ **Time:** _____

Thank you for participating in this study. Please answer the following questions.

1. On the diagram, please place an X on the area(s) that hurt the most.

2. Please rate your pain by filling in on the scale below the number that best describes your pain at its worst in the last 24 hours.

No Pain	—————→										Worst Possible
Pain											
0	1	2	3	4	5	6	7	8	9	10	

3. Please rate your pain by filling in on the scale below the number that best describes your pain at its least in the last 24 hours.

No Pain	_____→										Worst Possible Pain
0	1	2	3	4	5	6	7	8	9	10	

4. Please rate your pain by filling in on the scale below the number that best describes your pain on the average in the last 24 hours.

No Pain	_____→										Worst Possible Pain
0	1	2	3	4	5	6	7	8	9	10	

5. Please rate your pain by filling in on the scale below the number that best describes your pain right now.

No Pain	_____→										Worst Possible Pain
0	1	2	3	4	5	6	7	8	9	10	

6. In the past 24 hours, how much relief have pain treatments or medications provided? Please darken the circle that most shows how much relief you have received.

No Relief	_____→										Complete Relief
0	1	2	3	4	5	6	7	8	9	10	

7. In the past 24 hours, how many times did you experience nausea?

None	One	Two	Three	Four	Five	Six	Seven	Eight	Nine +
0	1	2	3	4	5	6	7	8	9

8. In the past 24 hours, how many times did you experience vomiting?

None	One	Two	Three	Four	Five	Six	Seven	Eight	Nine +
0	1	2	3	4	5	6	7	8	9

Please darken the number in the box that best describes the extent your pain has interfered with your daily activities. If you are unsure how to answer a question, choose the answer that comes closest to how you feel.

9. Static Pain

	No Interference	—————→ Complete										
Interference												
a. Lying in Bed	0	1	2	3	4	5	6	7	8	9	10	
b. Sitting up in Bed	0	1	2	3	4	5	6	7	8	9	10	
c. Laughing	0	1	2	3	4	5	6	7	8	9	10	
d. Coughing	0	1	2	3	4	5	6	7	8	9	10	
e. Sneezing	0	1	2	3	4	5	6	7	8	9	10	
f. Talking	0	1	2	3	4	5	6	7	8	9	10	
g. Singing	0	1	2	3	4	5	6	7	8	9	10	
h. Watching TV	0	1	2	3	4	5	6	7	8	9	10	

10. Moving Pain

Interference	No Interference	—————→ Complete									
a. Getting out of Bed	0	1	2	3	4	5	6	7	8	9	10
b. Bending	0	1	2	3	4	5	6	7	8	9	10
c. Bathing Yourself	0	1	2	3	4	5	6	7	8	9	10

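### Years 2 and 4 are meant to capture chronic pain, but the calendar schedules no analgesic record there, so treated pain cannot be told from absent pain

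*Combined protocol and SAP*

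**What the plan says.** Section 5.1, and the study design entry in the Section 1 summary, explain the late follow-up: "The Year 2 and Year 4 follow-ups are included as tertiary endpoints to capture differences in chronic pain". Section 5.1 adds that "patients will be asked to complete the same questionnaires as at the Day 90 follow up". Section 5.11 sets the mode of contact: "follow-up phone interviews will occur at post-operative Year 2", and likewise at Year 4.

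In Section 6, Table 3, the row "Pain Meds/Opioid Use" is marked at Pre-Study and Days 1, 2, 3, 7 and 90. Its cell for Years 2 and 4 is empty. That column is marked for "Update Medical History", the Patient Pain Assessment Questionnaire, the post-operative BREAST-Q, the RAND-36 and the Quick DASH.

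Opioid use is a secondary outcome in Sections 4.2 and 10.1.2. Section 10.2 plans descriptive statistics by arm for all primary, secondary and tertiary outcomes at time points that include Year 2 and Year 4. It also plans a survival analysis of time to stopping opioids.

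In Appendix A, the pain questionnaire, the only item that locates pain is a drawing: "On the diagram, please place an X on the area(s) that hurt the most".

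**The concern.** A pain score taken years after surgery is hard to interpret without knowing whether the woman takes analgesics. A low score may mean that the pain has gone, or that it persists and is treated. If the block reduced chronic pain, part of the effect could appear as less analgesic use and not as lower scores. With no record of use, that part would go unseen, and a null result on scores would be ambiguous.

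Opioid data would be easy to interpret here. Section 5.2.2 requires zero opioid use at baseline, so any opioid use found at Year 2 or Year 4 began after enrolment. Section 10 itself describes opioid use as a more objective measure of post-operative pain.

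Also at stake is agreement within the plan: Section 10.2 promises a summary of a secondary outcome at two time points for which the calendar schedules no collection.

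**Working it through.** The plan states no figure to reproduce on this point. The check sets the calendar beside the sections that depend on it.

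**1. Is analgesic use scheduled at Years 2 and 4?** Table 3 has eight visit columns. The analgesic row is marked in six: Pre-Study and Days 1, 2, 3, 7 and 90. The two empty columns are Surgery and Years 2 and 4.

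**2. Does anything else at Years 2 and 4 record it?**
- The medical history update has no stated medication content. At Days 1, 7 and 90 the calendar marks it and the analgesic row separately, so the first is not a stand-in for the second.
- Appendix A item 6 asks for perceived relief from treatments or medications over 24 hours. It records no drug, no dose and no yes/no answer on use.
- The sentence in Section 5.1 about repeating the Day 90 questionnaires does not clearly carry analgesic use forward, because the Day 90 list names it apart from the instruments. If it was meant to carry forward, Table 3 contradicts Section 5.1.
- The patient-recorded oxycodone and Tylenol data described in Section 10.2 stop at Day 7.

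**3. Does the analysis need it?** Opioid use is secondary (4.2, 10.1.2), and Section 10.2 summarises all secondary outcomes at Years 2 and 4. For time to stopping opioids, a woman still using them at Day 90 has no later scheduled record.

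**4. Is pain site available at Years 2 and 4?** Yes, from instruments that Table 3 schedules there and that can be answered aloud:

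| Source | Items | Content | Recall |
|---|---|---|---|
| Post-operative BREAST-Q, question 6 a-f | 6 | Pain in the neck, upper back, shoulder, arm, ribs, chest muscles (frequency) | 2 weeks |
| Post-operative BREAST-Q, question 6 l-p | 5 | Tenderness and sharp, shooting, aching, throbbing pain in the breast area (frequency) | 2 weeks |
| Quick DASH, item 9 | 1 | Arm, shoulder or hand pain (severity) | 1 week |

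That is 6 + 5 + 1 = 12 site-specific pain items. Question 3 of the pre-operative BREAST-Q has the same list, so change from baseline is available for the BREAST-Q items.

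**5. What lacks a site?** Appendix A items 2 to 5 give 0-10 intensity and name no body site. Their only locator is the diagram, and the plan gives no instruction for completing it by telephone.

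**6. How much data is affected?** 70 women × 2 contacts = 140 interviews at most, or 35 × 2 = 70 per arm, assuming complete follow-up.

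**The case against.** The strongest reply is that the late contacts already collect a good deal on pain. The 12 items above locate it, RAND-36 items 21 and 22 cover bodily pain over four weeks, and Appendix A asks for worst pain and for relief from medication. All of this stands, and it rules out two stronger readings.

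First, a reader might infer from the diagram and the telephone mode that pain site cannot be captured, so that chronic post-surgical pain cannot be separated from unrelated pain. The documents do not support this: BREAST-Q question 6 and Quick DASH item 9 do that work. The diagram itself may also be recoverable. Discharged patients already answer this questionnaire by telephone on Days 2 and 3, and nothing bars an interviewer from marking the drawing from a spoken description. What is missing is an instruction.

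Second, a reader might infer that chronic pain lies outside the tertiary objective, which begins "To determine if long-term changes in Quality of Life scores" and lists only the three instruments. But those instruments contain the pain items, and Section 10.1.3 says that women are kept for four years partly to obtain final pain scores. What remains is narrower: no item is named as the chronic-pain measure.

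It can also be said that the all-outcomes sentence in Section 10.2 is general, and that its opioid paragraph concentrates on the first week, so a late opioid summary may not have been intended. That is possible and would weaken the inconsistency. It would not help with interpreting the late pain scores. None of the scheduled instruments records analgesic use, so that part of the point is unanswered.

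**Conclusion.** The point holds in a limited form. Analgesic use is not scheduled at the two contacts whose stated purpose is chronic pain. Scores there cannot be read against medication, and the opioid summary that Section 10.2 implies has no data. The defect is one empty calendar cell affecting at most 140 interviews for a tertiary purpose. It does not touch the 6-hour primary endpoint.

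No numerical bias is claimed. The documents give no rate of late pain or late analgesic use, and analgesics need not bring a woman's score down to that of a woman without pain. The conclusion rests on two readings: that an empty cell in Table 3 means no collection, and that the medical history update does not include a medication record. If the case report form for that update does list analgesics, the data gap closes, but Table 3 should still show it.

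The absence of a site applies only to the Appendix A intensity scores taken by telephone. It should not be extended to the Year 2 and Year 4 contacts as a whole.

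**What to change.** 1. In Table 3, mark the analgesic row at Years 2 and 4, and ask about current pain medication and opioid use in the interviews already planned.
2. In Section 10.2, state that the chronic-pain measure at Day 90, Year 2 and Year 4 is the existing BREAST-Q question 6 and Quick DASH item 9 pain items, reported by arm together with analgesic use.

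No new pain-site question is needed, because those items already ask for site. The Appendix A intensity scores can be reported beside them as all-site scores.

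The cost is a protocol amendment with IRB approval and a slightly longer call. No visit or instrument is added.
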